6. ASSESSMENTS

6.1. Clinical Assessment

Patients will have a complete neurologic examination by the PI and their medical records will be reviewed including EMG/NCS. A documentation of the disease onset, potential cause, onset of balance problem, most recent fall, examination of muscle strength, reflexes and sensory exam will be done by the PI.

6.2. Outcome Assessments

6.2.1. Proprioception Measurement

Both minimum detectable change in joint position and position matching techniques will be used.

For minimum detectable change in joint position of the ankle, subject's foot will be placed on a foot pad with adjustable angle. The starting angle will be parallel to the floor. The angle will be changed by 2 degrees in each step and subject will be asked to report as soon as they feel a movement in their ankle with their eyes closed. Direction of movement will be at both dorsiflexion and plantar flexion.

For the matching position of the ankle, the footpad will be positioned in various angles ranging from 5 degree to 45 degree and will be asked to try to match the ankle on the other side with their eyes closed. The angle on the other foot will be measured and recorded. For the same-

side matching, subjects will be asked to remember than angle and try to reproduce it after the ankle is returned to the neutral position.

For measuring proprioception at the big toe, the experimenter will move the toe with steps of 2 degrees at a time and will ask subject to report any change as soon as felt with their eyes closed.

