2.2. Endpoints

Primary Endpoint

Minimum detectable angle of dorsiflexion and plantar flexion of the ankle.

Secondary Measures and Efficacy Endpoints

1. Time to sway when standing with feet together and eyes closed;
2. Vibratory threshold as measured by Rydel Seiffer graduated tuning fork;
3. Distance walked in a timed walk test;

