4.1. Inclusion Criteria

Subject eligibility should be reviewed and documented by an appropriately qualified member of the investigator's study team before subjects are included in the study.

Subjects must meet all of the following inclusion criteria to be eligible for enrollment into the study:

1. Evidence of a personally signed and dated informed consent document indicating that the subject (or a legal representative) has been informed of all pertinent aspects of the study;
2. Subjects who are willing and able to comply with scheduled visits, and study procedures and are able to read and participate in all study assessments;
3. Subjects with axonal predominantly sensory large-fiber distal symmetric polyneuropathy confirmed with EMG/NCS.
4. Subjects who are walking independently without use of cane or walker.
5. Subjects with impaired proprioception and/or vibration at the toes/ankle on routine neurologic examination.
6. Age older than 18 years;

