8. DATA ANALYSIS/STATISTICAL METHODS

8.1. Sample Size Determination

Based on the review of the literature, a sample size of 15-20 patients often time has been used to investigate the effect of tDCS. We plan to recruit 20 patients in this study.

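### Each ankle reading of the primary endpoint can only be 2, 4, 6... degrees, so small improvements are often scored as no change and a patient who detects the first step cannot improve

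*Combined protocol and SAP*

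**What the plan says.** The primary endpoint in Section 2.2 is "Minimum detectable angle of dorsiflexion and plantar flexion of the ankle". Section 6.2.1 (Proprioception Measurement) sets out how a reading is taken:

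- Start: "The starting angle will be parallel to the floor".
- Increment and response, with eyes closed: "The angle will be changed by 2 degrees in each step and subject will be asked to report as soon as they feel a movement".
- Directions: "Direction of movement will be at both dorsiflexion and plantar flexion".

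The section describes no finer step, adaptive staircase, repeat run or interpolation, and no rule for combining the two directions. The position-matching task in the same section is not tied to 2-degree readings, but it is not the primary endpoint.

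Section 8.1 states: "We plan to recruit 20 patients in this study". Section 8.2 names a repeated-measures ANOVA and does not say how tied or floored values are handled. Inclusion criterion 5 in Section 4.1 admits "Subjects with impaired proprioception and/or vibration at the toes/ankle on routine neurologic examination".

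**The concern.** The endpoint is a threshold in degrees, and the trial compares it within patients, before stimulation and after real and sham stimulation. The recording rule rounds every threshold up to the next multiple of 2 degrees. Two different things follow.

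- **Above 2 degrees**, a patient's improvement smaller than one step is recorded either as nothing or as a full 2 degrees, depending on where the threshold lay within its step. This adds noise and produces ties.
- **At or below 2 degrees**, there is no room to improve. Someone who goes from 1.9 to 0.6 degrees is scored 2 both times. This pulls the real-versus-sham difference towards zero.

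With 20 patients and no power calculation, the plan shows no margin for losing information in the measurement. If many thresholds are low, a real effect could be reported as none. The loss cannot be recovered after data collection.

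**Working it through.** **The plan's own figure.** The sample size of 20 cannot be reproduced. Section 8.1 rests it on the sizes of earlier studies and gives no effect size, SD, alpha or power.

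**Inputs from the documents.** Start 0 degrees (level); step 2 degrees (Section 6.2.1); N = 20 (Section 8.1).

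**Step 1, the grid.** With the angle counted from level, recorded = 2 × ceil(true/2), minimum 2. So 0.6 → 2, 1.9 → 2, 2.1 → 4.

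**Step 2, changes above the floor.** Take the true threshold as uniform within its step and let it improve by d < 2. The reading changes only if a multiple of 2 is crossed, so P(no change) = 1 - d/2.

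| True improvement d | Scored as no change |
|---|---|
| 0.25 | 1 - 0.125 = 88% |
| 0.5 | 75% |
| 1.0 | 50% |
| 1.5 | 25% |

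The remaining patients, a share d/2, score a full 2 degrees. The mean recorded change is (d/2) × 2 = d, so it is unbiased. The cost is variance: 2²/12 = 0.33 per reading. Treating the two rounding errors as independent, a difference gains 0.67, an SD of 0.82 degree.

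**Step 3, power for a proportional effect.** Assumptions, none from the documents: lognormal thresholds with between-patient log-SD 0.5 and session log-SD 0.3; 25% true reduction; one reading per condition; paired t-test, two-sided 5%, N = 20; 4000 simulated trials per setting. Monte Carlo standard error near 72% is √(0.72 × 0.28/4000) = 0.7 points. Ranges are between repeated runs. Unrounded power is about 72% at every median.

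| Median threshold (degrees) | At the 2-degree floor | Difference exactly 0 | Power, 2-degree steps |
|---|---|---|---|
| 1 | 88% | 89% | 7% |
| 2 | 50% | 63% | 47% |
| 3 | 24% | 49% | 59-62% |
| 4 | 12% | 40% | 64-67% |
| 6 | 3% | 30% | 69-70% |
| 8 | 1% | 23% | 71% |

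With 0.5-degree steps, power is 64-65% at median 1, 70% at 2, and 71% or more from 3 upward.

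Under this model the mean recorded difference at median 1 is 0.16 degree against a true 0.30. At median 2 it is about unchanged.

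**Step 4, power for a constant effect.** Assume instead a true 1-degree improvement for everyone and a within-patient difference SD of 1 degree, with the same between-patient log-SD of 0.5.

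| Median | Unrounded | 1-degree steps | 2-degree steps |
|---|---|---|---|
| 1.5 | 0.98 | 0.94 | 0.63 |
| 2 | 0.99 | 0.96 | 0.77 |
| 4 | 0.99 | 0.97 | 0.89 |
| 8 | 0.99 | 0.98 | 0.91 |

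With a difference SD of 2 degrees, unrounded and 2-degree power are 0.52 and 0.35 (median 1.5), 0.53 and 0.40 (2), 0.56 and 0.49 (4), and 0.57 and 0.50 (8).

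Without the added session noise, the mean recorded gain is 0.44 against a true 0.94 at median 1.5 (the true gain is capped for patients with very low thresholds), 0.70 against 0.98 at median 2, and 1.00 against 1.00 at median 4.

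**Step 5, averaging the two directions.** No combining rule is stated, so this too is an assumption, applied to the model of Step 3. With fully independent noise in each direction, 2-degree power is 77%, 88% and 91% at medians 2, 3 and 4, against 94% unrounded. The losses are 17, 6 and 3 points. With session noise shared between directions and an added direction log-SD of 0.2, 2-degree power is 10% at median 1 and 48% at median 2, against 63% unrounded.

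**The case against.** The strongest reply is that the damage depends on a quantity the documents do not supply. No baseline ankle threshold is given for any patient, and in Step 3 the loss runs from 65 points (72 - 7) to 1 point (72 - 71). That stands, and it rules out an unconditional claim.

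A reader might infer from criterion 5 that many patients will sit at the floor, because vibration loss alone, or loss at the toes alone, is enough for entry. The documents do not settle this. Section 3 describes patients with balance complaints who have both vibratory and proprioceptive loss, and criterion 3 requires large-fiber neuropathy confirmed by electrodiagnostic testing. Criterion 5 makes a low ankle threshold possible. It does not make it likely.

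Averaging dorsiflexion and plantar flexion would soften the loss at medians of 2 degrees or more. However, the plan states no averaging, each reading keeps its floor, and a median of 1 degree is not rescued. A larger effect would also help: with a 50% reduction and a single reading, power with 2-degree steps is 96% at median 2 and nearly 100% from 3 upward.

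Rounding up overstates each threshold by 0 to 2 degrees, but it does so in both sessions. Above the floor this largely cancels in the within-patient contrast.

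Finally, the rounding model takes displacement from level as the stimulus. Section 6.2.1 asks about feeling a movement, which could mean each separate step. If so, a smaller increment changes the stimulus as well as the rounding. This is fair, and the revised text has to deal with it.

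**Conclusion.** The 2-degree grid and floor follow from Section 6.2.1 as written and need no assumption beyond counting the angle from level. That sub-step changes are often scored as no change is also sound: at least half the time for improvements up to 1 degree when thresholds are uniform within a step.

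The effect on the trial is conditional. Under the proportional model with one reading per condition, the loss of power is:

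- large at medians of about 2 degrees or below (25 points at 2, 65 at 1);
- moderate at 3 (10 to 13 points);
- modest at 4 (5 to 8 points);
- negligible from 6 degrees upward.

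The last line depends on the effect growing with the threshold. With a constant 1-degree gain and a difference SD of 1 degree, 8 points are still lost at a median of 8 (0.99 to 0.91).

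Two stronger readings go too far. One is that the loss is large for any median up to 4 degrees; the figures do not show that. The other is that coarse steps bias the effect towards zero throughout; above the floor the mean change is nearly unbiased, and shrinkage arises only through patients at the floor, whose share is unknown. What remains is a plain gain in precision that the plan gives up.

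**What to change.** In Section 6.2.1:

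- Replace the 2-degree ankle increment with the finest the adjustable footpad allows, at most 1 degree and ideally 0.5.
- Use the same increment in both sessions and at every time point, and record the angle to that resolution.
- State that detection is judged on the angle from the starting position, because each single movement will be smaller.

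Staggering the starting angle while keeping 2-degree steps is not a substitute. Displacement from a start of 0 or 1 degree is still 2, 4, 6... degrees with the same floor, and a pad that cannot be set finer than 2 degrees cannot be offset by 1.

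The cost is a short edit to one section and a longer ankle test with more steps per run. No extra patients are needed. The change depends on the pad being settable below 2 degrees. The documents call its angle adjustable but do not give its resolution, so this should be confirmed first.

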Objective quantification of proprioception may improve early detection of proprioceptive loss and help quantify this loss with aging. Present methods of proprioception quantification predominantly involve measurement of kinesthesia (ability to detect movement) and joint position sense (JPS). A common measure of kinesthesia is the threshold for perception of slow passive movement. Determining the error associated with active or passive reproduction of a joint angle assesses JPS. The most common used measures are passive or active matching and minimum detectable change in position. For example, one method that has been used to measure the proprioception at the ankle is to place one foot on a footpad that is tilted using a torque machine with a fixed speed. Subjects are asked to report as soon as they feel any movement in their ankle and the direction of the move. The angle when the patient pushes the button is used as threshold of proprioception. The other way of measuring it has been putting the ankle in a range of angles and use the angle that the subjects can report the direction of movement correctly more than 75% of trials as the threshold. Matching technique is asking the patient to reproduce an angle in the joint, either on the same side or on the other side. All of these measures have their own downsides and studies have tried to validate them with controversial results. Overall, it appears that threshold reporting is more sensitive than matching techniques. Functional measures such as time to sway and times walk have also been used to evaluate the effect of treatments such as physical therapy and balance training[19-21].

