3. STUDY DESIGN

This study will be performed in patients with peripheral neuropathy who are walking independently, but have complains of balance problems such as recent falls or difficulty walking and show reduced vibratory and proprioceptive sensation during routine neurologic examination. These patients will be tested for proprioceptive and vibratory threshold at the toes and ankles before, during and after receiving anodal tDCS over sensory and motor cortices, as well as sham stimulation. Patients will be blinded and won't know if they are receiving actual stimulation or sham stimulation. Subjects will be asked to participate in 2 sessions. In one of the sessions, decided randomly, the sham stimulation will be applied and during the other session the real tDCS stimulation will be applied. Similar sets of assessments will be performed before, during and after application of real or sham stimulations.

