5. STUDY PROCEDURE

The tDCS portion of the experiment will begin with DC current (maximum of 2 mA) stimulation delivered through surface electrodes (TransQE from IOMED®, surface area: 25 cm²) using a Phoresor® II Auto (Model No. PM850, IOMED®, Salt Lake City, Utah 84120, USA). One electrode will be positioned above the left or right primary motor cortex, the other electrode over the forehead [27].

For sham stimulation the electrodes will be placed in the same way as for real tDCS in the absence of real stimulation, this means stimulation will be increased to a current strength near to perception threshold and will be decreased afterwards and set to 0 mA output for the period of 20 min. With this procedure participants are usually unable to differentiate between tDCS and sham stimulation [38].

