8.2. Analysis of Primary and Secondary Endpoints

A repeated measure ANOVA will be used to compare the outcome measures before the stimulation, after the real stimulation and after the Sham stimulation.

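### Section 8.2 tests before, real and sham together and does not name real versus sham as the efficacy contrast, so a change common to both sessions can give a significant result without any tDCS effect

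*Combined protocol and SAP*

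**What the plan says.** Section 8.2 is a single sentence. A repeated-measures ANOVA will "compare the outcome measures before the stimulation, after the real stimulation and after the Sham stimulation". It names no contrast, and no other section says that real versus sham is the test of efficacy. The closing paragraph of section 1.2 describes the comparison in the same three-part way.

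Section 3 describes two sessions per patient, one real and one sham, in random order with the patient blinded: "Similar sets of assessments will be performed before, during and after application of real or sham stimulations". There are therefore two pre-stimulation values per patient, while 8.2 has a single level for the time before stimulation.

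The primary endpoint (2.2) is the smallest detectable ankle angle, so a lower value is better. Under 6.2.1 the footpad starts parallel to the floor and moves in 2-degree steps, and the "subject will be asked to report as soon as they feel a movement in their ankle with their eyes closed". Section 6.2.1 asks for no direction answer and mentions no no-movement steps.

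**The concern.** With three levels, the ANOVA null hypothesis is that before, after real and after sham all have the same mean. It can be rejected because real differs from sham, or because both differ from before. Only the first is evidence for tDCS. The second is what practice or a placebo response would produce.

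The ankle measure offers a further route. A patient who becomes readier to say that movement was felt scores a lower angle without sensing any better. If this happens after both sessions, 8.2 as written does not stop the significant ANOVA from being reported as an effect of stimulation, although the sham session was included to rule that out.

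**Working it through.** **Inputs from the documents:** 20 patients (8.1); three conditions (8.2); 2-degree steps from a start parallel to the floor (6.2.1); a pre-stimulation assessment in each session (3). The plan gives no alpha, SD, effect size, false-report rate or number of runs, so it has no figure of its own to reproduce here.

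**Assumed:** two-sided alpha 0.05, and the values named in each step.

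**Step 1. Any shared shift.** Let real and sham both differ from before by d standard deviations, with within-patient correlation 0.5.
- The three means deviate from their average by 2d/3, −d/3 and −d/3. The sum of squares is 2d²/3.
- The error variance is 1 − 0.5 = 0.5.
- The noncentrality is 20 × (2d²/3) / 0.5 = 26.67d², for an F test on 2 and 38 degrees of freedom.

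| Shared shift d (SD) | Noncentrality | ANOVA significant (formula) | ANOVA significant (20,000 simulated trials) | Real versus sham significant (simulated) |
|---|---|---|---|---|
| 0 | 0 | 5% | 4.6% | 5.0% |
| 0.25 | 1.67 | 18.2% | 18.1% | 4.9% |
| 0.5 | 6.67 | 59.6% | 60.0% | 5.2% |
| 0.75 | 15.0 | 92.5% | 92.4% | 5.1% |
| 1.0 | 26.67 | 99.6% | 99.6% | 5.0% |

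**Step 2. How far earlier reporting could move the ankle score.** Let the true threshold be T degrees, so k = T/2 steps. Let p be the chance of a false report at each step below threshold, with a report certain at threshold. The mean score is 2 × [1 − (1 − p)^k] / p.

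| T (degrees) | Mean score, p = 0.10 | Mean score, p = 0.20 | Apparent gain |
|---|---|---|---|
| 2 | 2.00 | 2.00 | 0 |
| 4 | 3.80 | 3.60 | 0.20 |
| 6 | 5.42 | 4.88 | 0.54 |
| 8 | 6.88 | 5.90 | 0.97 |
| 10 | 8.19 | 6.72 | 1.47 |
| 12 | 9.37 | 7.38 | 1.99 |

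Gains are taken before rounding. Low thresholds have to be considered because 4.1 admits "Subjects with impaired proprioception and/or vibration at the toes/ankle on routine neurologic examination", so a patient can enter on vibration alone.

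**Step 3. The two tests under that model.** There were 4,000 simulated trials per cell, with 20 patients, 2, 4 or 6 runs averaged per assessment, and Normal noise of SD 1 to 3 degrees per averaged assessment. The shift was the same after real and sham, and one pre-stimulation value entered the ANOVA.

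| Rise in p after both sessions | ANOVA significant, T = 6 to 12 | ANOVA significant, T = 2 to 6 |
|---|---|---|
| 10% to 20% | 17% to 72% | 5% to 10% |
| 2% to 5% | 7% to 20% | 5% to 6% |

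With no rise (10% throughout), the ANOVA was significant in 3.6% to 5.4% of trials. Real versus sham did not exceed 6% in any cell, whether tested on post-stimulation values or on change from each session's own pre-stimulation value.

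**Step 4. How to use the two pre-stimulation values.** Simulated standard error of the real-versus-sham contrast in degrees (4 runs, SD 1, T = 6 to 12, p = 0.20 after both sessions):

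| Day-to-day SD (degrees) | Post only | Change score | Pre-value difference as covariate |
|---|---|---|---|
| 0 | 0.567 | 0.764 | 0.576 |
| 1 | 0.646 | 0.772 | 0.642 |
| 2 | 0.863 | 0.754 | 0.709 |

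The covariate form is best or within 0.01 of best in each row.

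**The case against.** **The design already controls for this.** Each patient has a sham session, the order is random, the patient is blinded, and section 5 says "participants are usually unable to differentiate between tDCS and sham stimulation". A change shared by both sessions cancels in real versus sham. This stands in full, but the protection belongs to that contrast and 8.2 does not say that the contrast carries the claim.

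**8.2 may intend a session-by-time analysis.** The interaction would then be the real-versus-sham test, with error near 5%. That is a sensible analysis, but 8.2 lists three conditions rather than two sessions at two times. If it is what is meant, the fix only writes it down.

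**The inputs are assumed.** They are, and the low-threshold, low-rate cells show almost no inflation. The gap in 8.2 does not depend on these values; only the size of the illustration does.

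**A stronger reading that a reader might infer** is that the unverified ankle report is itself the main error and biases the efficacy result. The documents do not support this. A bias in real versus sham would need a reporting shift specific to one session, and nothing in the documents shows one. Assessor masking is not stated, but that does not show that it is absent.

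Nor does section 1.2 commit the plan to a direction check. It surveys methods. In one, "Subjects are asked to report as soon as they feel any movement in their ankle and the direction of the move", yet the recorded threshold is simply the angle at the button press. Only the other scores correctness: "use the angle that the subjects can report the direction of movement correctly more than 75% of trials as the threshold". The same section judges that "threshold reporting is more sensitive than matching techniques", and 6.2.1 does use threshold reporting. Scoring only correct directions would also move the endpoint from detecting movement to discriminating direction.

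**Conclusion.** The point holds as a gap in 8.2 and should be corrected before data are seen. As written, a significant three-level ANOVA does not distinguish a tDCS effect from a change that follows either session.

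The size depends on the assumed shared shift: about 60% significant null trials at 0.5 SD, and 17% to 72% or 5% to 10% in the ankle illustration with false reports rising from 10% to 20%, according to the true thresholds. These figures are neither bounds nor expected error rates for this trial. Under the same assumptions real versus sham stays near 5%.

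The self-reported threshold is one possible source of a shared shift. It is not shown to bias real versus sham and is not an error in the plan.

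**What to change.** In 8.2, state that:
1. the efficacy claim rests on the within-patient real-versus-sham contrast in the post-stimulation ankle threshold;
2. the contrast is adjusted for each session's own pre-stimulation value, with the difference between the two pre-stimulation values as a covariate;
3. a significant before/real/sham test alone does not support an efficacy claim.

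This costs one or two sentences and slightly more analysis. Section 3 already provides for the data.

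Optional: in 6.2.1, ask the patient to name the direction and include a few no-movement steps, reported by session as a diagnostic of false reporting, without changing how the primary threshold is scored. Five no-movement steps per post-stimulation test give 5 × 20 = 100 per session. The standard error of a 10% versus 20% difference is then √(0.1 × 0.9/100 + 0.2 × 0.8/100) = 0.05, or 0.05 × √2 = 0.07 with a design effect of 2. The cost is a longer ankle test, which matters because section 1.2 describes effects on sensation lasting only minutes. The steps should therefore be few.
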